6.2 PREPARATION, HANDLING, STORAGE, AND ACCOUNTABILITY

6.2.1 Responsibilities

Only participants enrolled in the study may receive study intervention and only authorized site staff may supply, prepare, or administer study intervention.

The Investigator, the hospital pharmacist, or other personnel allowed to store and dispense the study treatment will be responsible for ensuring that the IMP/AxMP/device used in the clinical trial is securely maintained as specified by the Sponsor and in accordance with applicable regulatory requirements.

All IMP/AxMP/device will be dispensed in accordance with the Investigator's prescription, and it is the Investigator's responsibility to ensure that an accurate record of IMP/AxMP/device issued and returned is maintained.

Any quality issue noticed with the receipt or use of an IMP/AxMP/device (deficiency in condition, appearance, pertaining documentation, labeling, expiration date, etc.) must be promptly notified to the Sponsor. Some deficiencies may be recorded through a complaint procedure (see pharmacy manual and [Section 8.6.8](#)).

A potential defect in the quality of IMP/AxMP/device may be subject to initiation of a recall procedure by the Sponsor. In this case, the Investigator will be responsible for promptly addressing any request made by the Sponsor, in order to recall the IMP/AxMP/device and eliminate potential hazards.

Under no circumstances will the Investigator supply IMP/AxMP/device to a third party (except for DTP shipment, for which a courier company has been approved by the Sponsor), allow the IMP/AxMP/device to be used other than as directed by this clinical trial protocol, or dispose IMP/AxMP/device in any other manner.

6.2.2 Treatment accountability and compliance

Administration of the IMP/AxMP/device will be supervised by the Investigator or Subinvestigator.

The person responsible for dispensing IMP/AxMP/device is required to maintain adequate records of the IMP/AxMP/device. These records (eg, drug movement form) include the date the IMP/AxMP/device is received from the Sponsor, dispensed for participant, and destroyed or returned to the Sponsor.

The packaging batch number (PR Nr) on the vial must be recorded on the drug accountability form.

The person responsible for IMP/AxMP/device administration to the participant will record precisely the date and the time of the IMP/AxMP/device administration to the participant.

For dexamethasone PO and pomalidomide PO, a participant diary will be used to document all oral dexamethasone or pomalidomide (if not administered at the site level).

6.2.3 Return and/or destruction of treatments

Partially used and used IMP/AxMP/device will be destroyed at the study site according to the standard practices of the site after an accurate accountability has been performed and signed by the Investigator (or the Pharmacist). A detailed treatment log form of the destroyed study treatment will be established with the Investigator (or the Pharmacist) and countersigned by the Investigator and the Monitoring Team. Any study materials provided by the Sponsor (IMP and/or medical devices) must be retained for return to the Sponsor for investigation if subject to a product technical complaint (see [Section 8.6.8](#)).

The Investigator must not destroy the unused study treatment unless Sanofi provides written authorization.

6.2.4 Isatuximab subcutaneous formulation

All details of preparation and administration of isatuximab are provided in the Pharmacy Manual.

Storage of Isatuximab SC should be in a secure area with restricted access. Isatuximab is to be stored at +2°C to +8°C (36°F to 46°F), is not to be frozen, and is to be protected from light. All containers must be kept in their box until use.

For at-home administration, isatuximab will be provided by the site on Day 1 and stored similarly (without the secure area) for D-15 administration.

For first at-home administration, the participant will be followed 30 min after the injection. Subsequent follow-up is left as per investigator judgment.

6.2.5 Isatuximab intravenous formulation

For participant with IV administration, the appropriate volume of isatuximab will be diluted in a 250 mL infusion bag of 0.9% sodium chloride solution or 5% dextrose solution. Please refer to the Pharmacy Manual for more information.

See [Section 6.1.1.1.1](#) for more detailed description of dose and method of administration.

Storage of isatuximab IV should be in a secure area with restricted access in site. Isatuximab is to be stored at +2°C to +8°C (36°F to 46°F), is not to be frozen, and is to be protected from light. All containers must be kept in their box until use. No protection from light is required for storage in the infusion bags.

Details of the storage conditions for the diluted solution are provided in the Pharmacy Manual.

6.2.6 Pomalidomide

Countries, where commercial supplies are desirable based on the country specific regulatory requirements, Pomalidomide from commercial supplies can be used. Otherwise, it will be re-labeled by the Sponsor according to Good Manufacturing Practice guidelines before supplies are provided by the study sites.

When commercial supplies will be used:

- Please refer to package insert or SmPC for further details as regards to formulation, storage, and handling procedures.
- When applicable the Pomalidomide Pregnancy Prevention Plan (Appendix 15, [Section 10.15](#)) or the country specific risk management plan (in countries where pomalidomide is not supplied by the Sponsor) has to be followed to ensure adherence of the pregnancy risk mitigation plan already in place in addition to the protocol requirements.

For a regional or national emergency declared by a governmental agency that results in travel restrictions, confinement, or restricted site access, pomalidomide may be supplied at the site or from the PI/site/Sponsor to the participant via a Sponsor-approved courier company, where allowed by local regulations and agreed upon by the participant during the time the measures are applied.

Further details as regards to formulation, storage and handling procedures will be provided in Package Insert or SmPC of commercial study treatment.

6.2.7 Dexamethasone

Dexamethasone PO will be supplied and re-labeled by the Sponsor according to Good Manufacturing Practice guidelines before supplies are provided to the sites.

For a regional or national emergency declared by a governmental agency that results in travel restrictions, confinement, or restricted site access, dexamethasone may be supplied at the site or from the PI/site/Sponsor to the participant via a Sponsor-approved courier company, where allowed by local regulations and agreed upon by the participant during the time the measures are applied.

Further details as regards to formulation, storage and handling procedures will be provided in Package Insert or SmPC of commercial study treatment.

6.3 MEASURES TO MINIMIZE BIAS: RANDOMIZATION AND BLINDING

6.3.1 Blinding rules

Potential bias will be reduced by the following steps:

- During the trial, administration of isatuximab SC or IV will be open-label, and no attempts will be made to blind administration. An IRT centralized randomization system will be used to prevent the investigators from knowing in advance the study intervention assignment, as the randomization is the best method to avoid bias.
- Despite the open-label administration of treatments, assessment of efficacy outcomes will be based on objectively collected data, which are radiological assessments for tumor response and central laboratory assessment that will be reviewed by an IRC blinded to study intervention arms.
- During the course of the study, an external independent statistician will perform unblinded safety and efficacy analyses for the data review of DMC. Access to these data and analyses will be restricted to the DMC members.
- Blinding rules for the Sponsor study team will be detailed in a separate document.

6.3.2 Randomization

All eligible participants will be randomly assigned to a treatment group (either SC or IV arm) in a 1:1 ratio using an IRT. Participant assignment to a treatment group will be performed according to a stratified randomization list as follows:

- MM isotype (IgG versus non-IgG).
- Body weight (≤ 65 kg, >65 - ≤ 85 kg, and >85 kg).
- Number of prior lines (1-2 versus ≥ 3).

After each participant has completed the necessary screening visit procedures, the corresponding baseline eCRFs have been completed and the participant is deemed eligible for randomization by the Investigator or designee based on the laboratory evaluations as defined in the study flow chart ([Section 1.3](#)), the study site will contact the IRT.

Study intervention will be dispensed at the study visits summarized in the schedule of activities (SoA).

WARNING: Randomization will be blocked if study treatment is not available at site level. A minimum of time will be required between screening registration call and study treatment delivery at site level. Please consider this time between screening call and randomization call, which is indicated in the IRT manual.

Study treatment should be initiated within 3 working days after randomization.

6.4 STUDY INTERVENTION COMPLIANCE

6.4.1 Subcutaneous isatuximab at-home administration

Subcutaneous at-home administration will be performed by an HCP, after completing the questionnaire allowing for at-home administration (including vital signs and novel symptoms). For at-home administration, filling of this questionnaire should be recorded and in case at-home administration is not performed, reason should be collected.

Participants randomized in the SC arm will receive a participant diary. The purpose of the diary is to report potential ISRs during the first 9 cycles in the SC-arm.

6.4.2 Dexamethasone and pomalidomide

Compliance to dexamethasone and pomalidomide will be assessed by direct questioning during the site visits and documented in the eCRF. Participants will be asked to maintain a diary to record the doses of pomalidomide/dexamethasone (except those administered by the study nurse/Investigator). Deviation(s) from the prescribed dosage regimen should be recorded.

6.5 DOSE MODIFICATION

Dose modifications are permitted according to the guidelines described in this section.

The participant may have a dose omitted for any IMP within a cycle if toxicity occurs and the participant does not recover within 3 days after the planned day of planned infusion/administration. If a participant experiences several toxicities and there are conflicting recommendations, the most conservative dose adjustment recommended (dose reduction/omission/delay appropriate to the most severe toxicity) should be followed. Within a cycle, the treatment window is ± 1 day for each of QW IMP administrations and ± 3 days for each of Q2W IMP administrations.

Cycle delays are permitted in case of toxicity (see [Section 6.5.7](#)). Cycle is considered delayed if Day 1 is performed more than 3 days after the planned Day 1 of this cycle. Once a dose of IMP has been decreased, intra-participant re-escalation back to the previous dose level is not permitted, except for dexamethasone dose reduction in a context of intercurrent condition neither related to dexamethasone adverse event nor related to multiple myeloma that might require a transient dose reduction. If a dose reduction is required, it is to be applied compared to the last dose level received by the participant.

Administration of the IMP will be discontinued in the event of an AE that persists despite appropriate dose modifications or any other AE that, in the opinion of the Investigator, warrants discontinuation.

All changes to study treatment administration must be recorded in the eCRF. Participants will receive the next cycle of study treatment after recovery of the toxicity as described below. If one of the IMPs is permanently discontinued, the other IMPs can be continued until PD, unacceptable toxicity, or participant's wish to discontinue further study treatment. The end of study treatment in this case will be 30 days after the date of the last study treatment administration.

Recommendations for dose adjustments of IMPs due to AEs are described in [Table 13](#), [Table 14](#), [Table 15](#) (SC arm) and [Table 16](#).

6.5.1 Isatuximab

No dose reductions for isatuximab are permitted, but flow rate/infusion can be reduced, and dosing omissions are allowed in case of toxicity. Within a cycle, a delay of up to 3 days in cases of unresolved toxicity at the time of planned readministration is permitted; otherwise, the infusion is omitted.

6.5.2 Pomalidomide

Dose reduction steps for pomalidomide are shown in [Table 11](#). One or several doses of pomalidomide can be omitted.

Table 11 - Dose reduction steps for pomalidomide

Starting dose of pomalidomide (PO)	First dose reduction	Second dose reduction	Third dose reduction
4 mg	3 mg	2 mg	1 mg

6.5.3 Dexamethasone

For participants ≥ 75 years old, dexamethasone will be administered at 20 mg on Days 1,8,15 and 22 of a 28-day cycle. One or several doses of dexamethasone can be omitted, or the dose of dexamethasone can be decreased to every other week ([Table 12](#)).

Table 12 - Dose reduction steps for dexamethasone

Starting dose of dexamethasone Days 1, 8, 15 and 22 (PO)	First dose reduction	Second dose reduction	Third dose reduction	Fourth dose reduction
40 mg	20 mg	12 mg	8 mg	Discontinue dexamethasone
20 mg	12 mg	8 mg	4 mg	Discontinue dexamethasone

6.5.4 Dose adjustments according to adverse events

Dose adjustments for participants treated with isatuximab, pomalidomide and dexamethasone combination in the case of hematological adverse reaction are shown in [Table 13](#).

Table 13 - Guidelines for dose adjustments for hematologic toxicities - isatuximab/pomalidomide/dexamethasone combination

Adverse event	Recommended action		
	Isatuximab ^a (IV or SC)	Dexamethasone (PO)	Pomalidomide (PO)
Thrombocytopenia			
Thrombocytopenia Grade 3	Day 1 of cycle : delay until improvement $\geq 50 \times 10^9/L$ ^b and administer at same dose level ^c . Within cycle : maintain full dose of study treatment as planned. SC injection of isatuximab : at-home administration at D-15 should not be performed prior alignment with the investigator site.		
Thrombocytopenia Grade 4 with or without bleeding	Day 1 of cycle : delay until improvement $\geq 50 \times 10^9/L$ ^b and administer at same dose level ^c . Within cycle : delay isatuximab until bleeding is controlled and platelet recover $\geq 50 \times 10^9/L$ and then administer full dose. If delay is >3 days omit isatuximab and dexamethasone until next planned administration. SC injection of isatuximab : at-home administration at D-15 should not be performed prior alignment with the investigator site.	Day 1 of cycle : delay Day 1 administration until recovery and pomalidomide decreased by one dose level ^c . Within cycle : hold pomalidomide until bleeding is controlled and platelet recover $\geq 50 \times 10^9/L$, and then re-start with 1 dose level decrease up to planned Day 21. Next cycle will be restarted with this one dose level decrease. second episode : same recommendation with decrease of pomalidomide by a second dose level. third episode : discontinue pomalidomide.	
	Further episodes: same recommendation.		
Neutropenia			
Neutropenia Grade 3	Day 1 of cycle : delay until recovery absolute neutrophil count $\geq 1.0 \times 10^9/L$ and administer at same dose level ^c . Within cycle : maintain full dose as planned.		

Adverse event	Recommended action		
	Isatuximab ^a (IV or SC)	Dexamethasone (PO)	Pomalidomide (PO)
Neutropenia Grade 4 ^d	Day 1 of cycle: delay until absolute neutrophil count recovery $\geq 1.0 \times 10^9/L$ and administer at the same dose level ^c . Within cycle: Maintain same dose as planned. Further episodes: same recommendations.	Day 1 of cycle: delay Day 1 administration until recovery and restart pomalidomide decreased by one dose level or consider G-CSF use and keep same dose level. Within cycle: hold pomalidomide until neutrophil counts recover $\geq 0.5 \times 10^9/L$ and then: 
• Re-start with 1 dose level decrease up to planned Day 21. Next cycle will be re-started with this one dose level decrease.• Or consider G-CSF use and keep same dose level. Second episode: same recommendations with decrease of pomalidomide by a second dose level. third episode: discontinue pomalidomide.	
Febrile neutropenia and/or neutropenic infection	Day 1 of cycle: delay Day 1 administration until fever and infection recover and add G-CSF until $ANC > 1 \times 10^9/L$ ^c . Then administer Day 1 next cycle with isatuximab and dexamethasone at the same dose level and pomalidomide with dose recommendations below. Within cycle: omit isatuximab and dexamethasone, hold pomalidomide dose and add G-CSF until fever and infection have recovered and $ANC > 1 \times 10^9/L$. Then administer isatuximab and dexamethasone at the planned days at the same dose level and re-start pomalidomide up to planned Day 21 with dose recommendations below: 
• First episode, resume same dose pomalidomide with G-CSF or re-start with 1 dose level decrease.• Second episode, resume with action not done at first episode (same dose with G-CSF or 1 dose decrement pomalidomide).• Third episode, resume with one dose decrement of pomalidomide.• Fourth episode, stop pomalidomide.		

- a Participants may have isatuximab dose omission within a cycle if certain toxicities do not recover within 3 days following the day of planned infusion ([Section 6.5.1](#)).
- b For participants with plasma cells $> 50\%$ of bone marrow nucleated cells at baseline, to initiate Cycle 2, platelet counts should be $\geq 30\,000/mm^3$ regardless response status at end of Cycle 1. During Cycles 2-4, platelet counts should be $\geq 30\,000/mm^3$, if last response is not better than SD, but if last response is PR or better during Cycles 2-4, D1 next cycle can be administered only if platelet counts $\geq 50\,000/mm^3$. For D1 administration beyond Cycle 4, platelet counts should be $\geq 50\,000/mm^3$.
- c A dose delay of up to 14 days between cycles is permitted in order to recover to the participant's baseline status. Beyond 14 days, the participant should be discontinued from study treatment, unless there is strong evidence of clinical benefit to justify continuation of dosing with study treatment (see [Section 6.5.7](#)).
- d If G4 neutropenia, assess ANC every 2-3 days until ANC $\geq 0.5 \times 10^9/L$ and at least weekly thereafter until ANC $\geq 1.0 \times 10^9/L$.

IV: intravenous.
SC: subcutaneous.
PO: per os.

Dose adjustments for participants treated with isatuximab, pomalidomide and dexamethasone combination in the case of non-hematological adverse reaction are shown in [Table 14](#).

Table 14 - Guidelines for dose adjustments for non-hematologic toxicities - isatuximab/pomalidomide/dexamethasone combination

Adverse event	Recommended action		
	Isatuximab^c	Dexamethasone^c	Pomalidomide
DVT/PE			
Grade 3	
Day 1 of cycle: initiate appropriate anticoagulation therapy and when efficient anticoagulation administer cycle at full dose isatuximab and the same dose level of dexamethasone and pomalidomide^a.
 
Within cycle: maintain full dose isatuximab and the same dose level of dexamethasone as planned. For pomalidomide:
 
 First episode: hold pomalidomide, initiate appropriate anticoagulation therapy and restart same dose pomalidomide when efficient anticoagulation. Second episode: despite appropriate anticoagulation pomalidomide permanently discontinued. 		
Grade 4	
Day 1 of cycle: delay Day 1 administration until controlled and administer the full dose of isatuximab and the same dose level of dexamethasone^a.
 
Within cycle: delay isatuximab and dexamethasone until stabilization and resume without dose reduction at the next planned dates. If delay is >3 days omit isatuximab and dexamethasone until next planned administration.
		Pomalidomide permanently discontinued.
Peripheral Edema			
Grade ≥ 3 (limiting function and unresponsive to therapy or anasarca), excluding infusion associated reaction	
Day 1 of cycle or within cycle: maintain full dose isatuximab as planned.
	
Diuretics as needed, and decrease dexamethasone dose by 1 dose level.
 
if edema persists despite above measures, decrease dose another dose level.
 
If symptoms persist despite second reduction, dexamethasone permanently discontinued.
	
Day 1 of cycle or within cycle: maintain full dose pomalidomide as planned.

Allergic reaction/hypersensitivity			
Grade 2	
Hold study treatment until <Grade 2, and participant clinically stable; then, resume study treatment at the same dose level for infusion reaction related to isatuximab^a.
 
For allergic reaction related to pomalidomide, refer to site local protocol.
 
In case of D-15 at-home administration: transfer participant to investigator site.
		
Grade ≥ 3	Permanent discontinuation of the drug responsible of the allergic reaction.		
Grade ≥ 3 Infections without concomitant neutropenia	
Hold study treatment until systemic treatment of infection complete.
 
Resume all at the same dose level.
		
Herpes zoster	Hold study treatment until lesions are dry, then resume all at the same dose level.		

Adverse event	Recommended action		
	Isatuximab^c	Dexamethasone^c	Pomalidomide
Neuropathy			
Grade 2 with pain or Grade 3	Full dose isatuximab and same dose level of dexamethasone.	Hold pomalidomide until neuropathy improves to Grade \leq 2 without pain. First episode : resume pomalidomide with a decrease of pomalidomide by 1 dose level. Second episode : resume pomalidomide with a decrease by a second dose level. Third episode : pomalidomide permanently discontinued.	Hold pomalidomide until neuropathy improves to Grade \leq 2 without pain. First episode : resume pomalidomide with a decrease of pomalidomide by 1 dose level. Second episode : resume pomalidomide with a decrease by a second dose level. Third episode : pomalidomide permanently discontinued.
Grade 4	Full dose isatuximab and same dose level of dexamethasone.		pomalidomide permanently discontinued.
Confusion or mood alteration Grade \geq 2 (interfering with functions \pm daily activities)	Day 1 of cycle or within cycle : maintain full dose isatuximab as planned.	Hold dexamethasone until symptoms resolve. Restart with 1 dose level reduction. If symptoms persist despite above measures, dexamethasone permanently discontinued.	Day 1 of cycle or within cycle : maintain same dose level of pomalidomide as planned.
Gastrointestinal dyspepsia, gastric or duodenal ulcer, gastritis			
Grade 1-2 (requiring medical management)	Day 1 of cycle or within cycle : maintain full dose isatuximab as planned.	Treat with H2 blockers, sucralfate, or omeprazole. If symptoms persist despite above measures, decrease dexamethasone dose by 1 dose level.	Day 1 of cycle or within cycle : maintain same dose level of pomalidomide as planned.
\geq Grade 3 (requiring hospitalization or surgery)		Hold study treatment until symptoms adequately controlled. Then, restart full dose isatuximab and same dose level of pomalidomide, and decrease dexamethasone by one dose level of current dose along with concurrent therapy with H2 blockers, sucralfate, or omeprazole. If symptoms persist despite above measures, dexamethasone permanently discontinued.	
Acute pancreatitis	Dexamethasone permanently discontinued. Day 1 of cycle : delay Day 1 until recovery ^c and re-start full dose isatuximab and same dose level of pomalidomide. Within cycle : hold all study treatment until recovery and re-start full dose isatuximab and same dose level of pomalidomide.		
Hyperglycemia \geq Grade 3	Day 1 of cycle or within cycle : maintain full dose isatuximab as planned.	Treatment with insulin or oral hypoglycemic agents as needed. If uncontrolled despite above measures, decrease dose by one dose level until levels are satisfactory.	Day 1 of cycle or within cycle : maintain same dose level of pomalidomide as planned.

Adverse event	Recommended action		
	Isatuximab ^c	Dexamethasone ^c	Pomalidomide
Muscle weakness ≥Grade 2 (symptomatic and interfering with function ± daily activities)	Day 1 of cycle or within cycle: maintain full dose isatuximab as planned.	Decrease dexamethasone by one dose level. If weakness persists despite above measures decrease dose by one level. If symptoms persist dexamethasone permanently discontinued.	Day 1 of cycle or within cycle: maintain same dose level of pomalidomide as planned.
Renal dysfunction eGFR <30 mL/min/1.73m ² (MDRD formula)	Day 1 of cycle: delay Day 1 administration until eGFR returns to ≥30 mL/min ^a . Within cycle: hold study treatment until improvement to ≥30 mL/min. Then re-start full dose isatuximab, same dose level of dexamethasone and pomalidomide up to planned Day 21. If delay is >3 days, omit isatuximab and dexamethasone.		
Progressive multifocal leukoencephalopathy (PML)^d	If PML is suspected If PML is confirmed If PML is recovered	If PML is suspected If PML is confirmed If PML is recovered	If PML is suspected If PML is confirmed If PML is recovered
Any other drug related nonhematologic Grade 3-4 AE	Day 1 of cycle: delay Day 1 administration until recovery and apply same rules of dose modification than the rules below ^a . Within cycle: For isatuximab attribution, omit dose if the event has not recovered within 3 days. Resume at full dose when toxicity has improved to Grade 2 or less or to baseline grade. Second episode, isatuximab discontinuation. For dexamethasone attribution omit dose if the event has not recovered within 3 days. Resume with 1 dose level decrease when toxicity has resolved to Grade 2 or less or to baseline grade. Second episode, apply new dose reduction. Third episode, dexamethasone discontinuation. For pomalidomide attribution, hold dose. Resume with 1 dose level decrease when toxicity has improved to Grade 2 or less or recovered to baseline grade. Second episode, apply new dose reduction. Third episode, pomalidomide discontinuation.		

- a A dose delay of up to 14 days between cycles is permitted in order to recover to the participant's baseline status. Beyond 14 days, the participant should be discontinued from study treatment, unless there is strong evidence of clinical benefit to justify continuation of dosing with study treatment (see [Section 6.5.7](#)).
- b See [Section 6.1.2](#) for IR management. Participants may have pomalidomide one or several dose omission at any moment during the cycle.
- c Participants may have isatuximab and/or dexamethasone dose omission within a cycle if certain toxicities do not recover within 3 days following the day of planned infusion (see [Section 6.5](#)).
- d See [Section 6.1.1.3](#) for monitoring of PML and dose modification of study IMPs.

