6.8.1 Antithrombic therapy

Pomalidomide increases the risk of venous thromboembolism. Anticoagulation prophylaxis is required after an assessment of each participant's underlying risk factors. Unless there is an excess risk of bleeding (those participants are to be excluded from the study; see exclusion criterion E2) all participants should receive prophylactic antithrombotic treatment. Patients with known risk factors for thromboembolism – including prior thrombosis – should be closely monitored. Action should be taken to try to minimise all modifiable risk factors (eg, smoking, hypertension, and hyperlipidemia).

Aspirin prophylaxis is recommended for participants with standard risk. If aspirin is contraindicated, participants will receive another form of antithrombotic therapy according to hospital guidelines or physician preference. Participants with at least 1 risk factor (ie, history of prior venous thromboembolism, immobilization, and concomitant use of an erythropoiesis-stimulating agent) should use low-molecular weight heparin or alternatively a direct oral anticoagulant (factor Xa inhibitors, direct oral factor IIa inhibitors) or a vitamin K antagonist.

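### Grade 3 DVT/PE in Table 14: the rule to stop pomalidomide for good at a second episode is written only for events within a cycle, not for those managed at Day 1

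*Protocol*

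**What the plan says.** Table 14 in Protocol Section 6.5.4 gives two branches for Grade 3 DVT/PE.

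- **Day 1 of a cycle.** Anticoagulation is started and, "when efficient anticoagulation administer cycle at full dose isatuximab and the same dose level of dexamethasone and pomalidomide". First and later episodes are not distinguished. The footnote attached to this branch deals only with how long a cycle may be delayed (up to 14 days).
- **Within a cycle.** The instruction is to "maintain full dose isatuximab and the same dose level of dexamethasone as planned. For pomalidomide", followed by two bullets. At a first episode pomalidomide is held, anticoagulation is started, and the same dose is resumed. The second bullet reads "despite appropriate anticoagulation pomalidomide permanently discontinued".

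The next row, Grade 4 DVT/PE, has one pomalidomide outcome whatever the day: "Pomalidomide permanently discontinued". Section 6.8.1 gives the background: "Pomalidomide increases the risk of venous thromboembolism".

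**The concern.** The second-episode stop hangs on the lead-in that continues the within-cycle sentence, so as printed it belongs to that branch alone. The first bullet, to hold and then resume, also makes sense only in mid-cycle. A recurrent Grade 3 clot handled at Day 1 therefore has no stopping rule, and the one instruction printed for that day is pomalidomide at the same dose level.

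What is at stake is participant safety and consistent conduct. The protocol names pomalidomide as a cause of venous thromboembolism, and it treats recurrence under anticoagulation as reason enough to end the drug. Followed literally, the Day 1 branch allows re-exposure at the same dose in that situation. Two sites could manage identical recurrences in opposite ways and both comply.

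**Working it through.** This is a check of wording. The protocol states no figure to reproduce.

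**Step 1: the two branches side by side (Table 14, Grade 3 DVT/PE).**

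| | Day 1 of cycle | Within cycle |
|---|---|---|
| First episode | Anticoagulate, then same pomalidomide dose | Hold, anticoagulate, resume same dose |
| Second episode despite anticoagulation | Not addressed; the only instruction is the same dose | Pomalidomide ended permanently |

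The branches agree for a first episode and diverge for a second.

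**Step 2: is this how the tables usually work?** Six rows of Tables 13 and 14 have a pomalidomide rule that depends on episode number.

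- *Febrile neutropenia or neutropenic infection:* the Day 1 text points to the episode rules: "Then administer Day 1 next cycle with isatuximab and dexamethasone at the same dose level and pomalidomide with dose recommendations below".
- *Any other drug-related non-hematologic Grade 3-4 event:* the Day 1 text carries them over: "delay Day 1 administration until recovery and apply same rules of dose modification than the rules below".
- *Grade 4 thrombocytopenia and Grade 4 neutropenia:* the later episodes are separate entries listed after both branches.
- *Neuropathy:* there is no Day 1 split, so the rule applies on any day.
- *Grade 3 DVT/PE:* the episode rule is confined to the within-cycle branch.

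Count: 2 (express link) + 2 (listed after both branches) + 1 (no split) + 1 (confined) = 6. Five of the six reach Day 1 and this one does not.

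**Step 3: does another section close the gap?**

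- Section 6.5 requires the most conservative adjustment, but its condition is "If a participant experiences several toxicities and there are conflicting recommendations". A recurrent clot is one toxicity.
- Section 6.5 also has an IMP discontinued for an adverse event that persists despite dose modification, or for any other event that the investigator judges to warrant it. Recurrence is not clearly persistence, and the second limb is judgement.
- Section 7.1.1.1 lists unacceptable adverse events as a reason to stop, again on the investigator's opinion.
- The catch-all row of Table 14 does not apply, because DVT/PE has its own row.
- Section 6.8.1 covers prophylaxis and monitoring, not what to do after a recurrence.

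None of these gives a Day 1 rule for a second Grade 3 DVT/PE.

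**Step 4: size.** With 28-day cycles and onset spread evenly over the cycle (an assumption), the share of recurrences falling on Day 1 itself is 1/28 = 3.6%. A wider reading is possible. Pomalidomide is taken on Days 1 to 21, so for an event on Days 22 to 28 (7 days) there is nothing to hold and the next pomalidomide decision comes at Day 1. Counting those days gives (7 + 1)/28 = 28.6%, although by date such events are still within the cycle. Both figures are shares of second Grade 3 events, for which the protocol gives no rate.

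**The case against.** The best counter-argument is that the Day 1 sentence was never meant for recurrences. It tells the site to *initiate* anticoagulation, but a participant with a second event should already be anticoagulated. On that view the sentence is silent about recurrence and does not direct re-exposure. That is fair, but it moves the defect without removing it: a recurrence at Day 1 is then left with no rule, and same-dose pomalidomide is still the only Day 1 instruction on the page.

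Layout is a second point. The cell was read from a PDF, and in the Grade 4 thrombocytopenia and neutropenia rows the episode entries also follow the within-cycle text. In those rows, however, the episodes are separate entries at the level of the two branches. Here they are bullets under a lead-in that continues the within-cycle sentence. The text order is coherent and shows no sign of a lost Day 1 rule.

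Third, the tables are guidelines, the investigator can stop any drug for an event that warrants it, and the second-episode bullet is visible in the same cell. Most recurrences will also surface mid-cycle, where pomalidomide ends before the next Day 1. The sponsor probably meant the rule to cover both branches, and many investigators would apply it so. All of this stands as a limit on the practical risk. It does not supply the rule.

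**Conclusion.** The point holds. As printed, permanent discontinuation of pomalidomide at a second Grade 3 DVT/PE applies only within a cycle, and the Day 1 branch has no second-episode rule. It is the only one of the six rows with a pomalidomide episode rule to be confined in this way.

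The gap is small. It needs a second Grade 3 event in the same participant, handled at Day 1: 3.6% of such events on the strict reading with uniform onset. How many participants that means cannot be estimated from the protocol. Both arms follow the same rule, and neither the sample size nor the primary analysis is touched. It deserves correction because it leaves a safety stopping rule to discretion on one day of the cycle, for no stated reason.

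**What to change.** In the Grade 3 DVT/PE cell of Table 14, take the pomalidomide episode rule out of the within-cycle branch and state it once for both branches:

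- First episode: pomalidomide at the same dose level once anticoagulation is effective (held until then if the event occurs mid-cycle).
- Second episode despite appropriate anticoagulation: pomalidomide is permanently discontinued, whether the event is managed at Day 1 or within the cycle.

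The isatuximab and dexamethasone text stays as it is. The cost is one reworded table cell in the next amendment. No analysis or sample size text changes.
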